8.3. Prior and Concomitant Treatment

Reasonable efforts will be made to determine all relevant treatment (concomitant medications, including all prescription/non-prescription medications, herbal medications, vitamin supplements, supportive therapies, and concomitant non-pharmacological treatments) received by the subject within 14 days before administration of the first dose of study drug through the last study visit. These medications/treatments will be recorded in the eCRF. The medication name, route of administration, dose, unit, frequency and indication and duration of the treatment/procedure (start and stop dates) will be recorded in the eCRF.

8.3.1. Permitted Adjunctive Therapies

Minor surgical or bedside procedures (including incision and drainage, aspiration, lavage, etc.) are allowed during the study. However, planned major surgical procedures during the study that

could incur blood loss or fluid shifts are not permitted as this may impact the safety and PK analysis.

8.3.2. Prohibited Medications

As the safety data collection in this trial is extremely important, use of additional antibiotics during the study period should be minimized unless the patient is a treatment failure requiring unexpected rescue antibiotics or requires additional antibiotics to treat a new infection during the study.

9. STUDY DRUGS

9.1. Method of Assigning Subjects to Treatment Groups

The study is randomized 1:1 (Current Formulation:New Formulation). Randomization will take place in the electronic data capture (EDC) system once the subject is screened and confirmed to be eligible for participation.

9.2. Treatments Administered

After randomization, dosing will be performed on Day 1. All participants will receive a single intravenous infusion of oritavancin, either the current formulation or the new formulation, diluted as indicated below. A pharmacist or qualified designee will prepare the study drug infusions. No other material or diluent may be substituted or concomitantly infused through the same IV line. Refer to the Pharmacy Manual for further details regarding dose preparation and administration.

9.2.1. Current Oritavancin Formulation

The currently approved formulation is composed of 3 single-use vials, each containing 400 mg of oritavancin diphosphate (as the free base) and the inactive component mannitol. Oritavancin vials will be reconstituted with SWFI and further diluted in D5W for a total volume of 1000 mL and infused intravenously over 3 hours.

9.2.2. New Oritavancin Formulation

The new formulation is composed of a single vial containing 1200 mg of oritavancin, HP β CD, and mannitol. Oritavancin vials will be reconstituted with SWFI and further diluted with 0.9% sodium chloride (saline) for a total volume of 250 mL and infused intravenously over 1 hour.

9.3. Packaging and Labeling

The Sponsor will provide the current and new formulation. Infusion bags of D5W and 0.9% sodium chloride will be provided by the study site pharmacy.

Vial labels will comply with regulatory requirements. The storage conditions for each medication provided will be described on the medication label.

This study is open-label and therefore, the site personnel and study subject will know which formulation they are receiving and the infusion duration (3 hours or 1 hour). The pharmacist will label the infusion bag with the oritavancin 1200 mg (new formulation or current approved formulation) and will include the infusion time (1 hour or 3 hours).

9.4. Study Drug Storage Conditions

Oritavancin lyophilized powder should be stored at controlled room temperature (20°C to 25°C; 68°F to 77°F) in a secure cabinet. Diluted intravenous solution in an infusion bag should be used **within 6 hours when stored at room temperature, or within 12 hours when refrigerated.**

The combined storage time (reconstituted solution in the vial and diluted solution in the bag) and infusion time should not exceed 6 hours at room temperature or 12 hours when refrigerated (see Pharmacy Manual). Access should be strictly limited to the study pharmacists and their designees.

9.5. Blinding

The study is open-label and therefore, there is no blinding of the study drug or study drug infusion time.

9.6. Receipt of Supplies

Upon receipt of the investigational drug, the pharmacist or designated study site personnel will visually inspect the shipment and verify the drug information, quantity, and condition of the kits received. The Investigational Drug Transmittal and Receipt Form will be completed and signed by the pharmacist and retained in the pharmacy binder. In addition, receipt of the study drug shipment will be sent to Melinta for placement in the Trial Master File (TMF).

9.7. Study Drug Accountability

It is the responsibility of the Investigator to ensure that a current record of inventory/drug accountability is maintained. The investigator or designee must maintain an inventory record of all study medications received and administered to assure the regulatory authorities and the Sponsor that the drug will not be dispensed to any person who is not a subject under the terms and conditions set forth in this protocol. Drug accountability forms and/or specific instructions can be found in the Pharmacy Manual. Inventory records must be readily available for inspection by the study monitor and available to Regulatory Agencies for inspection at any time.

The oritavancin supplied for use in this study is to be prescribed only by the Principal Investigator or designated sub-investigators and may not be used for any purpose other than that outlined in this protocol.

During the study, all used oritavancin containers (e.g., empty vials) will be kept until the monitor has reviewed the accountability records. If this is not permitted by the institution's Standard Operating Procedures (SOP), this should be discussed with the monitor prior to study start.

9.8. Study Drug Handling and Return

Upon the completion or termination of the study, and upon written authorization from Melinta or its representative, all unused and/or partially used study drug should be returned or destroyed at the investigational site, as specified by Melinta. It is the Investigator's responsibility to ensure that Melinta or its representative has provided written authorization that procedures for proper disposal of the study drug have been established, and that appropriate records of the disposal are documented and maintained. No unused study drug may be disposed until fully accounted for by the Melinta monitor (or designee).

9.9. Product Complaints

Sites are required to report any product complaints to Melinta immediately but no later than 24 hours from the time of awareness, by phone or e-mail as follows:

US Phone: [name] ([name])

Email: [contact]

Product Complaint: Is defined as any written, electronic, or oral communication that alleges deficiencies related to the identity, durability, reliability, quality, safety, effectiveness or

performance of a product, after it is released for distribution (EU DIR 2001/83/EC). (Derived from Ref US 21 CFR 211.198)

There are two types of Product Complaints: Technical Quality Complaints and Preference Complaints.

Technical Quality Complaint: A report of dissatisfaction with the product with regard to its efficacy, strength, integrity, purity, or quality; thus, a potential failure to meet product specifications. Examples include:

- An indication that there is an unexpected physical change in the drug product such as discoloration, change in shape of the drug product, presence of particulates or any other physical change that might indicate contamination, a manufacturing defect or any other event that might indicate a compromise in product quality.
- An indication that the content does not meet its labeled volume, count, etc.
- An indication that there is an unexpected physical change in any part of the container (this includes the bottle, any part of the seal, the cap or the label).
- An indication that the product is mislabeled.
- An indication that there is an unexpected physical change of the product or container once the product is diluted or reconstituted (the container includes the vial, bag, IV-line, syringe or any other item that is in contact with the product).
- An indication that the product is falsified, tampered with or adulterated.
- An indication that the product did not meet its pharmacologic effect, i.e. lack of efficacy.

Preference Complaints: A report of dissatisfaction with service, delivery, packaging or other preference.

10. SCHEDULE OF ASSESSMENTS AND PROCEDURES

This study will consist of three periods:

1. Screening Period – within 48 hours prior to first dose
2. Day 1 (pre-dose, dosing, post-dose)
3. Follow-up Period – Day 2 through Day 15 (End of study visit)

The subject's participation from screening/informed consent to end of study will be up to approximately 17 days.

10.1. Schedule of Events/Assessments

The Schedule of Events/Assessments ([Table 4](#)) summarizes the study assessments by time point.

Table 4: Schedule of Events/Assessments

Study Procedures	Screening	Day 1		Follow-up Visit				Unscheduled Visit
	≤ 48 hrs prior to Day 1	Pre-Dose	Dosing	Post-Dose (1 hr or 3 hrs)	Day 2 (24 hrs)	Day 4 (72 hrs)	Day 8 (168 hrs)	
Informed consent	X							
Assess inclusion/exclusion	X	X						
Medical history, including microbiology results if available	X							
Randomize subject		X						
Physical exam including height & weight	X							X
Vital signs ¹	X	X		X			X	X
Urine pregnancy test ²	X	X						X X
Chemistry and hematology laboratory assessments ³	X						X X	X
Record prior or concomitant medications and surgical procedures	X	X		X X X X				X X X X
Administer IV oritavancin ⁴			X					
Direct & Indirect Coombs Test ⁵		X					X X	X
Collect plasma for oritavancin antibody assay ⁶		X					X X	X
Collect plasma for PK ⁷		X		X X X X				X
Assessment of adverse events ⁸			X X X X				X X X X	X

¹Vital signs include blood pressure, temperature, respiratory rate and heart rate.

²At Screening and Day 15, perform a local urine pregnancy test for female subjects of childbearing potential (may be omitted for females > 2 years postmenopausal or surgically sterile). A urine pregnancy test will be performed again on Day 1 for female subjects of childbearing potential if the screening pregnancy test was performed > 24 hours prior to dosing.

³Unless otherwise indicated, all chemistry and hematology laboratory tests will be performed by the site's local laboratory.

⁴Start time of study drug infusion is Hour 0 (study drug will be administered over 1 hour or 3 hours)

⁵Direct and Indirect Coombs testing will be done at the local laboratory. Samples will be collected at Day 1 (pre-dose), Day 8 and Day 15. If a subject has a change in Direct or Indirect Coombs results at Day 8, subjects may be asked to return for subsequent labs in order to investigate this change. Subjects with a positive Direct or Indirect Coombs test at the Day 15 visit must have the test repeated every 2 weeks until it returns to baseline or stabilizes.

⁶Plasma samples will be stored and tested for oritavancin antibody only if the subject(s) experience unexpected adverse events that may be associated with antibody production.

⁷Time points for PK sample collection are Day 1 pre-dose and at the end of infusion (1 hour or 3 hours), and then at 3 hours (for 1 hour infusions), 6 hours, 12 hours, 24 hours, 72 hours, and 168 hours after the start of the infusion. See [Table 5](#) for windows for PK draws and visits.

⁸Adverse events and serious adverse events will be assessed from the time of study drug administration through Day 15 post administration of oritavancin.

⁹If the subject is required to terminate the study early, the subject must complete the Day 15 assessments at the time of the Early Termination Visit.

10.2. Screening Period (Within 48 Hours Prior to Day 1)

The following procedures will be performed within 48 hours prior to study drug administration to assess subject eligibility for the study:

1. Obtain written informed consent.
2. Assess inclusion/exclusion criteria.
3. Record medical history including microbiology results, if available.
4. Perform a physical examination (including height and weight).
5. Obtain vital sign measurements (blood pressure, heart rate, respiratory rate and temperature).
6. A local urine pregnancy test will be performed for female subjects of childbearing potential (may be omitted for females > 2 years postmenopausal or surgically sterile).
7. Collect blood specimens for hematology and serum chemistry tests.
8. Record prior and concomitant medications and surgical procedures (this includes, but is not limited to, aspiration, debridement, incision and drainage).

10.3. Randomization

Randomization should only occur once subject eligibility criteria are confirmed (see Section [9.4](#)).

10.4. Day 1 (Pre-Dose)

The following assessments will be performed on Day 1 prior to dosing:

1. Assess inclusion/exclusion criteria.
2. Obtain vital sign measurements (blood pressure, heart rate, respiratory rate and temperature).
3. A local urine pregnancy test will be performed for female subjects of childbearing potential (may be omitted for females > 2 years postmenopausal or surgically sterile) if the screening pregnancy test was performed > 24 hours prior to dosing.
4. Record prior and concomitant medications and surgical procedures (this includes, but is not limited to, aspiration, debridement, incision and drainage).
5. Collect blood specimens for PK, Direct and Indirect Coombs testing and oritavancin antibody assay.

10.5. Day 1 (Dosing)

Oritavancin will be administered over 3 hours (if randomized to the current formulation) or over 1 hour (if randomized to the new formulation). The start time of study drug administration is Day 1 (Hour 0), and all subsequent visits and PK draws will be calculated from this start time.

All AEs and SAEs that occur during the infusion will be recorded. See Section [5.4.1.2](#) for guidance in the event a hypersensitivity or infusion-related reaction occurs during infusion.

10.6. Day 1 (Post-Dose)

The following assessments will be performed on Day 1 after dosing:

1. Obtain vital sign measurements (blood pressure, heart rate, respiratory rate and temperature).
2. Collect plasma for PK at the end of infusion (1 hour or 3 hours), and then at 3 hours (for 1 hour infusions), 6 hours, and 12 hours after the start of the infusion.
3. Record concomitant medications and surgical procedures (this includes, but is not limited to, aspiration, debridement, incision and drainage).
4. Assess AEs and SAEs.

10.7. Follow-up Visits Day 2 (24 Hours) and Day 4 (72 Hours)

The following assessments will be performed on follow-up visits at Day 2 and Day 4 (See [Table 5](#) for the **visit window** for each visit):

1. Collect plasma for PK at 24 hours (Day 2) and 72 hours (Day 4) after the start of the infusion.
2. Record concomitant medications and surgical procedures (this includes, but is not limited to, aspiration, debridement, incision and drainage).
3. Assess AEs and SAEs.

10.8. Follow-up Visit Day 8 (168 Hours)

The following assessments will be performed on the follow-up visit at Day 8 (See [Table 5](#) for the **visit window** for Day 8):

1. Obtain vital sign measurements (blood pressure, heart rate, respiratory rate and temperature).
2. Collect blood specimens for hematology and serum chemistry tests.
3. Record concomitant medications and surgical procedures (this includes, but is not limited to, aspiration, debridement, incision and drainage).
4. Collect blood specimens for Direct and Indirect Coombs testing and oritavancin antibody assay.
5. Collect plasma for PK at 168 hours after the start of the infusion.
6. Assessment of AEs and SAEs.

10.9. End of Study (Day 15/Early Termination Visit)

The following assessments will be performed on follow-up visit at Day 15 or the Early Termination Visit (See [Table 5](#) for the **visit window** for Day 15):

1. A local urine pregnancy test will be performed for female subjects of childbearing potential (may be omitted for females > 2 years postmenopausal or surgically sterile).

2. Collect blood specimens for hematology and serum chemistry tests.
3. Collect blood specimens for Direct and Indirect Coombs testing and oritavancin antibody assay.
4. Record concomitant medications and surgical procedures (this includes, but is not limited to, aspiration, debridement, incision and drainage).
5. Assessment of AEs and SAEs.

A subject's participation in the study is complete when the subject has completed the Day 15 Visit or Early Termination Visit. However, if at this visit there is an ongoing SAE, or the subject has a positive Direct or Indirect Coombs test, then the SAE will be followed and/or Coombs test result will be repeated up to a return to baseline condition or stabilization.

10.10. Unscheduled Visit

If at any time the Investigator believes the subject requires additional testing/follow-up, an Unscheduled Visit may be performed.

11. PROTOCOL ASSESSMENTS

11.1. Demographic Data/Medical History

Demographic information will be recorded at Screening. A complete medical and surgical history, including past and current use/abuse of drugs, alcohol, and tobacco, and any available microbiology results, will be collected at Screening and reviewed for any changes at Day 1. The medical history should include clinically significant medical or surgical history ongoing at baseline or with onset in the previous 2 years.

11.2. Adverse Events

Subjects will be carefully monitored for AEs by the investigator during the designated study period (see Section 13 for details).

11.3. Vital Signs

Vital signs (blood pressure, heart rate, respiratory rate and temperature) will be assessed at the designated time periods as indicated in the Schedule of Events (Section 10.1). Blood pressure and pulse must always be taken after the subject has been resting supine for 5 minutes.

11.4. Physical Examination

A complete physical examination, including height (cm) and weight (kg), will be performed at Screening. The complete physical examination will include the following organ or body system assessments: skin; head, neurological; lungs; cardiovascular; abdomen (liver, spleen); lymph nodes; and extremities.

11.5. Laboratory Assessments

Specimens will be obtained at the designated time periods as indicated in the Schedule of Events (Section 10.1). All safety laboratory assessments and Direct and Indirect Coombs Testing will be performed by the site's local laboratory. Additional local laboratory testing may be performed at the discretion of the investigator. Any clinically significant lab findings that occur during the study should be followed until returning to normal or baseline, or to a level that is agreed upon by both the Principal Investigator and the Sponsor. Laboratory assessments include:

- Chemistry: Blood urea nitrogen, Serum creatinine, Total bilirubin, Direct bilirubin, Alkaline phosphatase, Aspartate aminotransferase, Alanine aminotransferase, Albumin, Total protein, Glucose, Calcium, Chloride, Sodium, Magnesium, Potassium, Uric acid, Lactate dehydrogenase, Bicarbonate, Phosphorus.
- Hematology: Hemoglobin, Hematocrit, White blood cell count (with automated differential), Red blood cell count, Platelet count, Absolute reticulocyte count, Haptoglobin.
- Pregnancy Test: A urine pregnancy test (human chorionic gonadotropin for female subjects of childbearing potential only) will be conducted at Screening (and possibly at Day 1 if the screening test was performed more than 24 hours prior to dosing) and Day 15. For information about reporting occurrences of pregnancy in a study subject or a

study subject's partner (to be followed until conclusion of pregnancy and reported on specific forms; see Section 13.4.5.2).

- Direct and Indirect Coombs Test: Direct and Indirect Coombs Test will be conducted at Day 1 (pre-dose), Day 8 and Day 15.
- Oritavancin Antibody Assay: Two plasma samples will be collected at each of the following time points: Day 1 (pre-dose), Day 8 and Day 15. These samples will be stored at the site, and sent to a Central Lab for oritavancin antibody testing only if the subject(s) experiences unexpected AEs that may be associated with antibody production.

11.6. Assessment of Pharmacodynamics

Pharmacodynamic assessments will not be performed in this study.

11.7. Assessment of Pharmacokinetics

Blood samples for the analysis of oritavancin in plasma will be collected on Day 1 pre-dose and at the end of infusion (1 hour or 3 hours), and then 3 hours (for 1 hour infusions), 6 hours, 12 hours, 24 hours, 72 hours, and 168 hours after the start of the infusion. Every effort should be made to collect all PK samples at the optimal sample time (within the window in Table 5 below). The date and time of each PK sample will be recorded on the eCRF.

Table 5: PK Blood Draw Schedule

PK Blood Draw Schedule		
Optimal Sample Time from START of infusion	Sample Time Window	
	Lower Limit	Upper Limit
Pre-Dose (-30 minutes)	Any time prior to dose administration	Any time prior to dose administration
1 hour (end of infusion) New Formulation Arm Only	1 hr	1 hr 5 min
3 hours New Formulation Arm Only	2 hrs 50 min	3 hrs 10 min
3 hours (end of infusion) Current Formulation Arm Only	3 hrs	3 hrs 5 min
6 hours	5 hrs 45 min	6 hrs 15 min
12 hours	10 hrs	14 hrs
24 hours (Day 2)	20 hrs	28 hrs
72 hours (Day 4)	60 hrs	84 hrs
168 hours (Day 8)	Day 7	Day 9

Detailed collection, processing, storage, and shipment procedures will be provided in PK sample collection laboratory manual. Samples will be sent to a central laboratory for analysis. Plasma

concentrations will be determined using liquid chromatography-tandem mass spectroscopy methods.

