5.4.1.2. Hypersensitivity and Infusion Related Reactions

Serious hypersensitivity reactions have been reported with the use of oritavancin. If an acute hypersensitivity reaction occurs during oritavancin infusion, discontinue oritavancin immediately and institute appropriate supportive care. Due to the possibility of cross-sensitivity, carefully monitor for signs of hypersensitivity during oritavancin infusion in patients with a history of glycopeptide allergy. In the Phase 3 ABSSI clinical trials, the median onset of hypersensitivity reactions in oritavancin-treated patients was 1.2 days and the median duration of these reactions was 2.4 days.

Infusion related reactions have been reported with the glycopeptide class, including oritavancin. The reactions resemble "Red-man Syndrome", including pruritus, urticaria and/or rash and flushing of the upper body. If infusion-related reactions occur, slowing or interrupting the infusion could stop the reaction.

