5.4.1.3. Other Potential Risks

Oritavancin has been shown to artificially prolong prothrombin time (PT) and International Normalized Ratio (INR) for up to 24 hours, making the monitoring of the anticoagulation effect of warfarin unreliable up to 24 hours after an oritavancin dose. Subjects currently receiving anticoagulant therapy are excluded from this study at Screening.

Infusing oritavancin in a shorter duration may result in a higher C_{max} . A higher C_{max} may produce adverse events (AEs) similar to those observed in the oritavancin cardiac safety study ([MDCO-ORI-12-02](#)) where 1600 mg infused over three hours was selected as the supratherapeutic dose. In this study, forty-eight healthy volunteers were administered the 1600 mg supratherapeutic oritavancin dose (current formulation) and seven reported oral paresthesia or oral hypoesthesia. They were of mild intensity as were most of the events reported from the 1600 mg dose.

There are no additional AEs expected from using HP β CD as the excipient in this trial.

A complete description of relevant risks of oritavancin can be found in the Investigator's Brochure ([Oritavancin Investigator's Brochure Edition 12.0](#)).

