Pre-Dose (-30 minutes)	Any time prior to dose administration	Any time prior to dose administration
1 hour (end of infusion) New Formulation Arm Only	End of Infusion	End of Infusion + 5 min
3 hours New Formulation Arm Only	2 hrs 50 min	3 hrs 10 min
3 hours (end of infusion) Current Formulation Arm Only	End of Infusion	End of Infusion + 5 min
6 hours	5 hrs 45 min	6 hrs 15 min
12 hours	10 hrs	14 hrs
24 hours (Day 2)	20 hrs	28 hrs
72 hours (Day 4)	60 hrs	84 hrs
168 hours (Day 8)	Day 7	Day 9

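### Protocol and SAP time the end-of-infusion PK draw differently, so an overrunning infusion may be sampled while drug is still running and its Cmax read too low

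*Protocol*

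**What the plan says.** **Protocol.** Section 11.7, Table 5, counts sample times from the start of infusion. The row "1 hour (end of infusion) New Formulation Arm Only" has limits of 1 hr and 1 hr 5 min, and the row "3 hours (end of infusion) Current Formulation Arm Only" has limits of 3 hrs and 3 hrs 5 min. Section 10.5 supports the clock reading: "all subsequent visits and PK draws will be calculated from this start time". The row labels, the text of sections 10.6 and 11.7, and footnote 7 of Table 4 nevertheless call this an end-of-infusion sample, with the nominal time in brackets.

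**SAP.** Section 7, Table 2, keeps the same rows but replaces the clock limits. Both windows open at the end of infusion and close at "End of Infusion + 5 min".

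**Infusions that run long.** Protocol 5.4.1.2 says of infusion reactions that "slowing or interrupting the infusion could stop the reaction", and section 10.5 refers sites to that guidance. SAP 8.5.4 counts dose interruptions. The PK population (Protocol 14.3.2.2, SAP 8.3.2) requires the full dose and sets no limit on infusion duration.

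**Status of the endpoints.** AUC0-72 and AUC0-168 are primary. Cmax and Tmax are exploratory.

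**The concern.** The two windows coincide only when the infusion lasts exactly its nominal time. Beyond a 5-minute overrun they no longer overlap. Site staff then have to choose between the clock limits and the row label, and different sites may choose differently.

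A draw taken on the clock in such a subject is a mid-infusion concentration. It would enter the Cmax and Tmax summaries as if it were the peak. The documents do not say what to do with it: a valid sample is not defined, SAP 8.4.3 includes all collected data, and the PK deviation listed in Protocol 15.3 is two or more consecutive missed draws, so one mistimed draw is not covered. A missed peak cannot be recovered afterwards.

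At stake is the description of peak concentration under the shorter infusion, a quantity that Protocol 5.4.1.3 singles out.

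**Working it through.** **1. The plan's own figure.** The documents give no figure for Cmax error. Their one design calculation is power for AUC equivalence. With CV 30%, the log-scale SD is √ln(1 + 0.30²) = 0.2936. With 50 per arm, SE = 0.2936 × √(2/50) = 0.0587. Two one-sided 5% tests on 98 df against 80-125% give 89.5%, 96.7% and 90.2% at true ratios 0.95, 1.0 and 1.05, as stated.

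**2. Do the windows overlap?** For an infusion of actual length T, the new-arm protocol window is 60 to 65 min and the SAP window is T to T + 5 min. They share a point only if T ≤ 65 min when the infusion overruns. In the current arm the limit is 3 h 5 min.

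**3. Model for the size.** Inputs are from Protocol Table 1 (approved formulation, means): half-lives 2.29, 13.4 and 245 h; AUC0-24 1110, AUC0-72 1530 and AUC0-∞ 2800 h·µg/mL. The rate constants kᵢ = ln 2 / half-life are 0.3027, 0.0517 and 0.00283 per hour. Solving the three AUC equations for a 3-hour infusion gives coefficients cᵢ = 134.9, 42.96 and 4.311 µg/mL. During a constant-rate infusion of length T,

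C(t) = Σ cᵢ (1 − e^(−kᵢt)) / (kᵢT), for t ≤ T.

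Observed Cmax is the highest value at the scheduled draws; the true peak is C(T).

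**4. Worked case, T = 1.5 h.** The terms cᵢ/kᵢ are 445.7, 830.5 and 1523.9.
- At 1 h: (116.4 + 41.9 + 4.3)/1.5 = 108.4 µg/mL.
- At 1 h 5 min: 116.3. At the scheduled 3 h draw: 111.4.
- True peak at 1.5 h: (162.6 + 62.0 + 6.5)/1.5 = 154.1.
- Shortfall with a 60-min draw: 1 − 111.4/154.1 = 27.7% (the 3 h sample is then the highest). With a 65-min draw: 1 − 116.3/154.1 = 24.5%.

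**5. Other durations, same model.**

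| Arm | Actual duration | True peak | Observed Cmax low by |
|---|---|---|---|
| New | 70 min | 159.6 | 6-13% |
| New | 75 min | 158.2 | 12-18% |
| New | 90 min | 154.1 | 24-28% |
| New | 120 min | 146.3 | about 20% |
| Current (draw at 3 h) | 3.5 h | 126.8 | 10% |
| Current (draw at 3 h) | 4 h | 121.3 | 18% |
| Current (draw at 3 h) | 4.5 h | 116.3 | 24% |

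New-arm ranges run from a 65-min to a 60-min draw. The shortfall shrinks beyond about 90 minutes because the 3 h draw becomes the highest sample. Three alternative fits that use the Table 1 Cmax of 138 µg/mL in place of one of the AUCs move the 90-min, 60-min-draw figure only to 28.4-28.7%.

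**6. Stop and resume at full rate.** The new-arm worst case is 30-31%, with a pause of about 0.35 h. In the current arm, a 1.5 h pause after a quarter of the dose gives 26-27%, and longer pauses can give more.

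**7. Draw at the actual end.** The loss is nil, or at most 1 − 2^(−(5/60)/2.29) = 2.5% if drawn 5 minutes late (alpha-phase decay).

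**8. AUC.** With the linear-up/log-down rule, a clock draw in the new arm makes AUC0-72 at most about 2.8% lower, and AUC0-168 at most about 2.3% lower, than an actual-end draw in the same subject.

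**9. Arm level, illustration only.** If n of 50 subjects each lose 28% of Cmax, the geometric mean falls by 1 − 0.72^(n/50): 0.7%, 1.3% and 3.2% for n = 1, 2 and 5. For AUC0-72, 1 − 0.972^(n/50) gives 0.06%, 0.11% and 0.28%.

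**The case against.** **The protocol calls this an end-of-infusion draw.** A reader might infer that slowed or interrupted infusions will be sampled mid-infusion. The documents do not go that far. A site could follow the label, draw at the actual end and accept a missed window. Table 5 is a best-effort target, and detailed collection steps sit in a laboratory manual outside these documents. This stands: mid-infusion sampling is possible, not certain, and the protocol is ambiguous within itself as well as at odds with the SAP.

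**Overruns may be rare.** In the earlier healthy-volunteer study, Tmax ranged over 1.00-1.04 h and 0.96-1.00 h in the two 60-minute cohorts, and the only infusion-related reaction listed was in the 30-minute cohort. This is fair but weak evidence: none in 16 subjects is compatible with a rate up to 1 − 0.05^(1/16) = 17% (one-sided 95% limit).

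**The error is not downward for everything.** It is for Cmax. For AUC0-72 against the model's true value at 90 minutes, the clock draw reads +1.6% and the actual-end draw +4.2%. An on-time 60-minute infusion on this schedule reads +4.3%, so for AUC the actual-end draw buys comparability between subjects, not accuracy.

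**The safety link is an inference.** A reader might conclude that the shortfall hides high peaks in subjects with infusion reactions. Protocol 5.4.1.3 links higher Cmax to oral paresthesia and hypoesthesia; section 5.4.1.2 describes infusion reactions separately, as a class effect. Slowing also lowers the true peak (162.6 to 154.1 µg/mL at 90 minutes), and the SAP plans no Cmax-by-event analysis.

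**Mistimed samples can be identified.** Draw times are recorded and the SAP summarises infusion duration. That allows flagging, but it does not restore the peak.

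**Conclusion.** The conflict is real but minor. For any infusion that overruns by more than 5 minutes, the protocol and SAP windows are incompatible, and a draw that complies with the protocol window precedes the end of infusion. In an affected new-formulation subject the modelled Cmax shortfall is about 6-13% at 70 minutes, rising to 24-28% at 90 and about 20% at 120. For a 3-hour infusion lasting 3.5 to 4.5 h it is about 10-24%.

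These percentages are illustrative. They apply approved-formulation mean half-lives to the new formulation (the alpha half-life alone has a CV of 49.8%) and assume durations and uniform slowing. None is a document figure, and 28% is not a ceiling, since stop-and-resume infusions can be somewhat worse.

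The frequency of overruns is not given, so no effect on the arm's mean Cmax can be derived. The documents do not support reading this as a threat to the equivalence conclusion: the 90% CI criterion applies to AUC, where the difference is under 3% per affected subject.

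**What to change.** Reconcile the two tables:

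- Restate both end-of-infusion rows of Protocol Table 5, and footnote 7 of Table 4, relative to the recorded actual end of infusion, as SAP Table 2 already does. Qualify the sentence in section 10.5 that counts every draw from the start time.
- Record the actual end-of-infusion time alongside the draw time.
- Add one sentence to SAP 8.5.6: a sample drawn before the actual end of infusion is flagged and not taken as the end-of-infusion value for Cmax or Tmax.

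The cost is a wording change or a site memo, plus one recorded time if it is not already captured. No extra draw is needed, and dosing and clinical management are untouched.
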